9.10. Other aspects

Not applicable.

10. PROTECTION OF HUMAN SUBJECTS

10.1. Study Participant information

All parties will comply with all applicable laws, including laws regarding the implementation of organizational and technical measures to ensure protection of participant personal data. Such measures will include omitting participant /HCP names or other directly identifiable data in any reports, publications, or other disclosures, except where required by applicable laws.

Participant/ HCP personal data will be stored at a secure online data collection software in encrypted electronic form and will be password protected to ensure that only authorized study staff have access. Redacted will implement appropriate technical and organizational measures to ensure that the personal data can be recovered in the event of disaster. In the event of a potential personal data breach, Redacted shall be responsible for determining whether a personal data breach has in fact occurred and, if so, providing breach notifications as required by law.

To protect the rights and freedoms of natural persons with regard to the processing of personal data, when study data are compiled for transfer to Pfizer and other authorized parties, any HCP names will be removed and will be replaced by a single, specific, numerical code. All other identifiable data transferred to Pfizer or other authorized parties will be identified by this single, participant-specific code.

Redacted will maintain a confidential list of HCPs who participated in the study, linking each HCP's numerical code to his or her actual identity. In case of data transfer, Pfizer will maintain high standards of confidentiality and protection of patients' personal data consistent with the research agreement and applicable privacy laws.

10.2. Study Participant consent

Due to the nature of the study, informed consent is not required. Participants need to go to the survey website in order to complete the survey. Consent is implied by these actions. Additionally, at the beginning of the survey, the respondent is asked if he/she agrees to take part in the survey. If yes, the respondent continues with the survey questions. If no, the survey is terminated.

10.3. Participant withdrawal

Any participant who will not complete all survey questions will be considered as withdrawal from the study.

10.4. Institutional review board (IRB)/Independent ethics committee (IEC)

Not applicable.

10.5. Ethical conduct of the study

The study will be conducted in accordance with legal and regulatory requirements, as well as with scientific purpose, value and rigor and follow generally accepted research practices described in Guideline on GVP Version 3.1 30-January-2023 - Drug Sector, SFDA.

11. MANAGEMENT AND REPORTING OF ADVERSE EVENTS/ADVERSE REACTIONS

This study does not involve data collection on individual patients by their treating HCPs and the DCT used in this study does not intend to identify product safety information. The DCT for this study will be completed online via a secure website. The DCT does not provide a free text field where study participants could specify information that may constitute product safety information. Further, routine communication with study participants via email or phone with is not expected during the conduct of the study. However, it is possible that a study participant may volunteer product safety information to Record while in conversation about the DCT for any other reason (e.g., seeking information about the purpose of the study); this information must be reported as described below.

The following safety events must be reported on the NIS AEM Report Form: serious and non-serious AEs when associated with the use of the Pfizer product, and scenarios involving exposure during pregnancy, exposure during breast feeding, medication error, overdose, misuse, extravasation, lack of efficacy and occupational exposure (all reportable, regardless of whether associated with an AE), when associated with the use of a Pfizer product.

For exposure during pregnancy in studies of pregnant women, data on the exposure to Vfend® (voriconazole) during pregnancy, are not reportable unless associated with serious or non-serious adverse events.

In the event that a study participant volunteers product safety information, complete the NIS AEM Report Form and submit to Pfizer DSU within 24 hours of becoming aware of the safety event. Included in the completion of the NIS AEM Report Form is the study participant's contact information; complete contact information should be obtained so that, once the NIS AEM Report Form is sent to Pfizer, the NIS AEM Report Form can be assessed and processed according to Pfizer's standard operating procedures, including requests for follow-up to the study participant.

team who will serve to be available to study participants to answer questions during study participant completion of the data collection tool, address any query from participants about the study must complete the following Pfizer training requirements:

"Your Reporting Responsibilities (YRR) with Supplemental Topics".

These trainings must be completed by team prior to the start of data collection. All trainings include a "Confirmation of Training Statement" (for signature by the trainee) as a record of completion of the training, which must be kept in a retrievable format. The study vendor will also provide copies of all signed training statements to Pfizer.

12. PLANS FOR DISSEMINATING AND COMMUNICATING STUDY RESULTS

A final report describing the survey objectives, detailed methods, results, discussion, and conclusions will be developed at the end of the survey for submission to SFDA within the timeframe specified in Section 6 'MILESTONES'.

In the event of any prohibition or restriction imposed (eg, clinical hold) by an applicable Competent Authority in any area of the world, or if Redacted is aware of any new information which might influence the evaluation of the benefits and risks of a Pfizer product, Pfizer should be informed immediately.

In addition, Redacted will inform Pfizer immediately of any urgent safety measures taken by the redacted to protect the study participant against any immediate hazard, and of any serious breaches of this NI study protocol that Redacted becomes aware of.

14. LIST OF TABLES

Not applicable.

15. LIST OF FIGURES

Not applicable.

16. ANNEX 1. LIST OF STAND-ALONE DOCUMENTS

Number	Document Reference Number	Date	Title
1.1		16 August 2024	Abstract
1.2		16 August 2024	HCP Questionnaire
1.3		16 August 2024	Invitation letter
1.4		16 August 2024	Follow up letter
1.5		16 August 2024	Assessment of success

Annex 1.1. Abstract

Title

Evaluation of the effectiveness of additional risk minimisation measures (aRMMs) that aim to reduce the risks of phototoxicity, squamous cell carcinoma (SCC) of the skin and hepatic toxicity in patients receiving voriconazole in the Saudi Arabia.

Protocol version and date

Version 1.0 16 August 2024

Name and affiliation of main author

Rationale and Background

Pfizer Saudi Limited will conduct a non-interventional, cross-sectional survey of healthcare professionals (HCPs) to evaluate the effectiveness of the aRMMs being implemented across Saudi Arabia to mitigate the risks of phototoxicity, SCC of the skin and hepatic toxicity in patients prescribed voriconazole (Vfend®), a broad spectrum triazole antifungal agent used to treat or prevent a range of serious fungal infections in both inpatient and outpatient settings.

To ensure that the risks are adequately managed, aRMMs in Saudi Arabia have been implemented since February 2023. The aRMM material distribution has been started on 05-February-2023 and continued until 05-February-2024 to the relevant HCPs who may initiate or manage patients on Vfend[®]. These include an updated voriconazole Summary of Product Characteristics (SPC)¹ (routine) and a new comprehensive education programme at the point of patient care that will educate/remind HCPs about the risks of phototoxicity, SCC of the skin and hepatic toxicity and how to manage them. The details of the Risk Minimisation (RM) tools for the educational programme and how these tools will be implemented across Saudi Arabia are described in the Risk Management Plan (RMP). The RM tools are the HCP Checklist, HCP Question & Answer (Q&A) Brochure and Patient Alert Card. HCPs who the materials are targeting will be invited to participate in the survey. The start of the data collection is intended to be within 18-24 months period from the launch of Vfend[®] in Saudi Arabia to allow physicians time for familiarity and use of the materials before evaluating the effectiveness of Vfend[®] aRMM.

Research Question and Objectives

The overall objective is to evaluate the effectiveness of the aRMMs to mitigate the risks of phototoxicity, SCC of the skin and hepatic toxicity in patients using voriconazole. The

Redacted

evaluation is being conducted in Saudi Arabia where RM tools are being implemented. Specifically, the objectives of the study are to:

- 4. Assess HCPs' awareness of the RM tools (i.e., HCP Checklist, HCP Q&A Brochure and Patient Alert Card).
- 5. Assess HCPs' utilization of the RM tools (i.e., HCP Checklist, HCP Q&A Brochure and Patient Alert Card)
- 6. Assess HCPs' knowledge of the risks of phototoxicity, SCC of the skin, and hepatic toxicity with voriconazole.
- 7. Assess whether HCPs' self-reported behaviour/practices with respect to minimizing the risks of phototoxicity, SCC of the skin, and hepatic toxicity are in accordance with the voriconazole SPC.¹

Study Design

This is a non-interventional, cross-sectional study to evaluate the effectiveness of RM tools for voriconazole. The study objectives will be accomplished by means of a cross-sectional, web-based survey of all HCPs who were targeted to receive the aRMMs and self-report as prescribers of voriconazole within 12 months preceding the survey in Saudi Arabia (Central, East and North regions). The study aims to obtain completed surveys from 10 HCPs. Data will be collected until 10 completed surveys are obtained or up to a data collection period of 60 to 90 days as a maximum. The data from the HCPs will be collected using a structured self-administered questionnaire to gather evaluation metrics related to the utilization and understanding of RM tool content and messages. In addition, the survey will assess behaviors, including a set of hypothetical scenarios for HCPs. The survey is not intended to be a mechanism for collecting adverse events (AEs), nor is it intended to result in minimizing the numbers of AEs reported. HCPs will be invited by e-mail to participate in the survey and asked to complete the online questionnaire.

Population

The target polulation will include all HCPs who were targeted to receive Vfend® aRMM materials within 12 months preceding the survey.

Inclusion criteria

- 1. Willing/consent to participate in this self-administered survey.
- 2. Involved in the treatment of at least one patient with voriconazole within the last 12 months.

Exclusion criteria

The HCPs meeting any of the following criteria will not be included in the survey:

- 1. Employed in full-time research or hospital administration (i.e., non-practising physicians).
- 2. Employment by Pfizer Inc or any research organization/vendor contracted by Pfizer to administer the survey.

Variables

Screening questions

- Consent to participate.
- Whether the HCP managed patient(s) treated with voriconazole during the last 12 months period preceding the survey.
- Employment by Pfizer or any research organization/vendor contracted by Pfizer to administer the survey.
- Participation in qualitative research of the VFEND (voriconazole) Risk Minimisation materials

The following variables will be collected through the HCP survey:

HCP demographics and medical mackground

- 1. Location
- 2. Primary medical specialty
- 3. Length of professional practice as a HCP

HCP knowledge on voriconazole toxicities:

- 1. Knowledge testing for specific risks associated with voriconazole treatment
- 2. Knowledge of treatment discontinuation recommendations and dealing with toxicities

RM tools receipt

- 1. Acknowledge receiving Q&A brochure
- 2. Acknowledge receiving HCP checklist
- 3. Acknowledge receiving Patient alert card

RM tools reading

- 1. Acknowledge reading Q&A brochure
- 2. Acknowledge reading HCP checklist
- 3. Acknowledge reading Patient alert card

RM tools utilization

- 1. Frequency of using HCP checklist, Q&A brochure, and Patient alert card
- 2. Ranking the usefulness of each RM tool

Self-declared behavior/practice

- 1. Patient counseling
- 2. Discussing risks with patients
- 3. Liver function monitoring
- 4. Dermatological evaluation
- 5. Treatment discontinuation recommendations

Other variables

- 1. Requesting extra RM tools
- 2. Number of patients treated with voriconazole in the past 12 months
- 3. Downloading the tools from website

Endpoints

- 1. The proportion of targeted HCPs who acknowledge receiving each of the RM tools (i.e., HCP Checklist, HCP Q&A Brochure and Patient Alert Card).
- 2. The proportion of targeted HCPs who acknowledge reading and utilizing the tools.
- 3. The proportion of targeted HCPs' who respond correctly to questiontions about the risks of phototoxicity, SCC of the skin, and hepatic toxicity.
- 4. The proportion of targeted HCPs who respond correctly to the practice-related questions and self-declared behavior with regard to strategies to mitigate the risks.

Data Sources (Survey)

A structured self-administered questionnaire comprised of closed-ended questions or statements with multiple response choices (i.e., questions or statements asking the HCPs to choose from a predefined list of responses) will be used to collect the survey data. The questionnaire will collect data on HCP characteristics in addition to their responses pertaining to the effectiveness of the aRMMs. It is estimated to take 20 to 25 minutes to complete the HCP questionnaire.

Study Size

At the time of protocol writing, a total of around HCPs (distribution list shared with the Saudi Food and Drug Authority [SFDA]) are expected to initiate or manage patients on Vfend®. All HCPs who were targeted to receive the RM tools (per Pfizer Inc.'s Distribution List.) within the 12 months preceding the initiation of the survey will be invited to participate in the survey. Given this relatively small pool of HCPs, an empirical sample size of 10 HCPs is proposed. Data will be collected until 10 completed surveys are obtained or up to a data collection period of 60 to 90 days as a maximum. It is important to note that the final survey sample size will depend on HCPs' willingness to participate in the survey.

An a priori threshold of 80% correct responses per risk question will be used to define the success of the program. However, this criterion will not be used for formal statistical testing. The selection of this threshold for success was regarded as being subjective and not based on prior knowledge, experience, or established scientific criteria.

Data Analysis

Detailed methodology for summary and statistical analyses of data collected in this study will be documented in a Statistical Analysis Plan (SAP), which will be dated, filed and maintained by the Sponsor. The SAP may modify the plans outlined in the protocol; any major modifications of primary endpoint definitions or their analyses would be reflected in a protocol amendment.

Data collected from the survey will be reported as descriptive statistics. Frequency distributions with 95% confidence intervals (CIs) will be calculated for HCPs' responses to all questions that address the survey objectives.

Milestones

In accordance with the SFDA Guideline on Good Pharmacovigilance Practices Module XVI (Risk minimisation measure: selection of tools and effectiveness indicators 30 January 2023)¹, data collection will begin after initial implementation of a RM programme in Saudi Arabia in February 2023 within 18-24 months), in order to allow the possibility of necessary amendments following the initial distribution of the approved RM tools in Saudi Arabia. This period will allow for the time required for utilization of the tools in Saudi Arabia health care

system. The planned timeline is contingent upon the date of the finalization and distribution of the RM tools within Saudi Arabia and the protocol endorsement by the SFDA.

Annex 1.2. HCP Survey Questionnaire

SURVEY LEGEND

- **[PROGRAMMER]** is used to indicate directions to the programmer and is set in bold, red, uppercase letters between square brackets.
- [BEGIN SURVEY CONTENT] and [END SURVEY CONTENT] are used to indicate to the programmer the type of survey administration and the beginning and end of the survey.
- **[TERMINATE]** is displayed next to responses that should cause the survey to end. The following termination language will be programmed into the survey or read by the interviewer.
 - Thank you for your time today. Based on your answer, you are not eligible to take part in this survey.
- **[GO TO Qx]** (skip logic) is inserted after a response to indicate to the programmer that the survey should skip to the indicated question (for example, **[GO TO Q17]** skips to question 17). If no skip logic is indicated the survey continues to the next question in the sequence.
- **[FREE TEXT]** indicates to the programmer that one line should be provided for data entry.
- [MULTILINE INPUT] indicates to the programmer that multiple lines should be provided for data entry (for example, two address lines).

[PREAMBLE 2]

VFEND® (voriconazole) Healthcare Professional (HCP) Survey

Please provide a response to all questions and statements.

1. Do you agree to take part in this survey?

□ Yes

		No [TERMINATE]
2.	Have mont	e you managed patient(s) treated with VFEND (voriconazole) within the past 12 ths?
		Yes
		No [TERMINATE]
3.		you currently employed by Pfizer Saudi Limited or United BioSource oration?
		Yes [TERMINATE]
		No
4.		you ever participated in qualitative research of the VFEND (voriconazole) Minimisation materials?
		Yes [TERMINATE]
		No
5.	Wha	t is your primary medical specialty?
		Critical Care
		Haematology
		Infectious diseases
		Intensive Care
		Microbiology
		Oncology
		Solid Organ Transplant
		Clinical pharmacist
		Non-clinical pharmacist
		Other Subspecialty: (Specify) [FREE TEXT]

		Other: (Specify) [FREE TEXT]
5a.	Whe	ere do you practice as an HCP?
		Dahran
		Dammam
		Hail
		Jeddah
		Jubail
		Khamis Mushait
		Khobar
		Madinah
		Makkah
		Najran
		Qurayat
		Riyadh
		Tabuk
		Taif
		Other: (Specify) [FREE TEXT]
6.	For	how long have you been practicing as an HCP?
		≤5 years
		6-15 years
		>15 years

7. According to the SPC/PI, the known risks for VFEND (voriconazole) are as follows: (Please select only one response for each of the risks listed in the table below.)

	Yes	No	I Don't Know
Phototoxicity (eg, skin rash)			
Intestinal perforation			
Squamous cell carcinoma (SCC) of the skin			
Asthma			
Hepatic toxicity			
Cardiomyopathy			

8. Please select only one response for each statement about VFEND (voriconazole) below:

	True	False	I Don't Know
Long-term treatment (>6 months) with VFEND (voriconazole) should be considered only if the benefits outweigh the potential risks			
If phototoxic reactions occur, multidisciplinary advice should be sought and the patient should be referred to a dermatologist			
VFEND (voriconazole) should not be discontinued if premalignant skin lesions or skin Squamous Cell Carcinoma are identified			
Laboratory evaluation of hepatic function (specifically AST and ALT) at initiation and during the first month of treatment with VFEND (voriconazole) is not necessary			
If the Liver Function Tests become markedly elevated, VFEND (voriconazole) should be discontinued , unless the medical judgment of the risk-benefit balance of the treatment for the patient justifies continued use			

9.		you or your hospital receive the VFEND (voriconazole) Healthcare Professional P) Q&A Brochure?
		Yes
		No [GO TO Q10]
		I don't remember receiving it [GO TO Q10]
DISP	LAY '	THE FOLLOWING IMAGE ON THE SAME PAGE NEXT TO Q9]
		VFEND®(Voriconazole) Oral/Intravenous Healthcare Professional Question & Answer Brochure
		NFIDENTIAL Version 2, December 2022 SAU-0064 Page 2
9.1.	Did :	you read the VFEND (voriconazole) HCP Q&A Brochure ?
		Yes, all of it
		Yes, some of it
		No, I did not read it
		I don't remember reading it
		Redacted

Page 39 of 53

Voriconazole A1501110 NON-INTERVENTIONAL STUDY PROTOCOL Version 1.0, 16 August 2024

10.	Did you or your hospital receive copies of the VFEND (voriconazole) Healthcare
	Professional (HCP) Checklist?

Yes
No [GO TO Q11]
I don't remember receiving it [GO TO Q11]

|DISPLAY THE FOLLOWING IMAGE ON THE SAME PAGE NEXT TO Q10

VFEND® (Voriconazole) Healthcare Professional Checklist

Please complete this Checklist at each visit with your patient being treated with VFEND® (Voriconazole). Each of the three sections includes important risk information followed by a series of check boxes to help in the management of your patient for whom you prescribed VFEND.

A) Minimizing the Risk of Phototoxicity and Skin Squamous Cell Carcinoma

- VFEND has been associated with phototoxicity and pseudoporphyria. It is recommended that all patients, including children, avoid exposure to direct sunlight during VFEND treatment and use measures such as protective clothing and sufficient sunscreen with high sun protection factor (SPF).
- The frequency of phototoxicity reactions is higher in the paediatric population. As an evolution towards SCC has been reported, stringent measures for the photoprotection are warranted in this population of patients. In children experiencing photoaging injuries such as lentigines or ephelides, sun avoidance and dermatologic follow-up are recommended even after treatment discontinuation.
- Squamous cell carcinoma (SCC) of the skin has been reported in patients taking VFEND, some of whom have reported prior phototoxic reactions.
- If phototoxic reactions occur, multidisciplinary advice (e.g. a consultation with a dermatologist) should be sought
 for the patient. VFEND discontinuation and use of alternative antifungal agents should be considered.
- Dermatologic evaluation should be performed on a regular basis whenever VFEND is continued, despite
 occurrence of phototoxicity-related lesions to allow early detection and management of premalignant lesions.
- VFEND should be discontinued if premalignant skin lesions or skin SCC are identified.
- SCC has been reported in relation with long-term VFEND treatment. Treatment duration should be as short as
 possible. Long- term exposure (treatment or prophylaxis) greater than 180 days (6 months) requires
 careful assessment of the benefit risk balance and physicians should therefore consider the need to limit
 the exposure to VFEND.
- For prophylaxis use, dose adjustments are not recommended in the case of lack of efficacy or treatment-related
 adverse events. In the case of treatment-related adverse events, discontinuation of VFEND and use of
 alternative antifungal agents must be considered.

Refer to the Summary of Product Characteristics for full prescribing and adverse event information.

Please review and answer the questions below for each patient receiving	og VEEND:
△ Has your patient developed phototoxicity? If YES, please refer to the Summary of Product Characteristics (SmP	YES NO
△ Have you arranged regular dermatologic evaluation for the patient presented with phototoxicity? If YES, please refer to the SmPC for further details. If NO, regular dermatologic evaluation should be arranged promptl details.	

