9.9. Strengths and Limitations of the Research Methods

9.9.1. Strengths

1. Web-based surveys

Redacted

Web-based surveys have been selected as the preferred research approach because:

- The HCP survey includes behavioral scenario-based questions that might be difficult to implement using other approaches.
- Web-based surveys can be answered at the participant's convenience so that an interview does not need arranging this can increase a participant's motivation to do the survey (improving response rates), thus resulting in more consistent completion of surveys.
- Web-based surveys are programmed to ask standardized questions and should elicit more consistent and reliable results than questions asked by telephone interviewers.
- Web-based techniques allow for a degree of interactivity to be introduced into the survey (e.g., logic to ask follow-on questions or not ask irrelevant questions), which strengthens the validity of the behavioral scenarios.
- 2. Questionnaire design and testing
- The web questionnaires include general questions followed by specific ones. They include both open and closed questions. As the HCPs may understand the right answer in subsequent questions, it will not be possible to go back in the questionnaire and edit answers in former questions.
- The questionnaires will be tested for their clarity. It will also be checked whether there are questions which would suggest a specific answer for any reason.
- 3. Experience in drug safety and the evaluation of RM measures

The study will be conducted by an experienced team specialized in the design and conduct of such surveys. It follows SOPs, as well as the methodological guidelines from SFDA Guideline on GVP.

4. Quality control and compliance

Quality controls are implemented on a regular basis by our teams.

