21.		often do you perform a dermatologic evaluation when VFEND (voriconazole) ntinuously used despite the occurrence of phototoxicity-related lesions? Weekly Monthly Every two months
		On systemic and regular basis
		I do not know
22.		which of below condition(s) would you discontinue VFEND (voriconazole) in a nt? (Select the one best response).
		Phototoxicity
		Squamous Cell Carcinoma (SCC)
		Premalignant lesions
		All of the above

23. Did you or another staff member request additional copies of the VFEND (voriconazole) RM tools?

Redacted

Voriconazole A1501110 NON Version 1.0, 16	-INTERVENTIONAL STUDY PROTOCOL August 2024
	Yes
	No
[CLOSING	
	Thank you.

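### The image at Q10 shows Checklist content before the practice questions and cues about 6 of the 16 objective 4 items, all concerning the skin risks

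*Protocol*

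**What the plan says.** Annex 1.2 places an image beside each receipt question. At Q9 (Q&A Brochure) and Q11 (Patient Alert Card) the text carried by the image is title or cover text. At Q10 the instruction is "DISPLAY THE FOLLOWING IMAGE ON THE SAME PAGE NEXT TO Q10", and the image is the first of three Checklist pages, with the section headed "A) Minimizing the Risk of Phototoxicity and Skin Squamous Cell Carcinoma" and its check-box questions. Among its statements are:

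- patients should "avoid exposure to direct sunlight during VFEND treatment and use measures such as protective clothing and sufficient sunscreen with high sun protection factor (SPF";
- "Dermatologic evaluation should be performed on a regular basis whenever VFEND is continued, despite" phototoxicity-related lesions;
- "VFEND should be discontinued if premalignant skin lesions or skin SCC are identified".

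The image is on the Q10 page itself, so respondents who answer that they did not receive the Checklist, or do not recall it, see it before being routed to Q11.

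Section 9.4 assigns Q18, Q18a, Q19, Q20, Q21 and Q22 to objective 4, and all of them come after Q10. Annex 1.5 counts an HCP as successful on practice only if every sub-question is answered desirably, and counts the objective as met if at least 80% of HCPs succeed. Section 9.7 also requires a count and proportion for each practice question separately. Section 9.9.1 recognises that later questions may reveal answers to earlier ones, and responds that "it will not be possible to go back in the questionnaire and edit answers in former questions".

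**The concern.** Objective 4 asks what HCPs report doing in practice. A respondent who has just read the tool's own advice can recognise the desired option a few screens later whatever their usual practice is. An HCP who never saw the Checklist in the field is shown the same page, so a desirable answer to a cued item is weaker evidence about the distributed material.

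The no-return rule works in one direction only. It protects Q7 and Q8, which precede the image. It does nothing for questions that follow it. The limitations in Section 9.9.2 cover selection, non-response, recall, social desirability and positional bias, but not this cue.

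With 10 planned respondents, each HCP is worth 10 percentage points, so two cued answers move an item from 60% to 80%.

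**Working it through.** **No planned figure to reproduce.** Section 9.5 calls the sample of 10 empirical. The check is a match of text to items, followed by an illustration on assumed rates.

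**Step 1: number of scored items.** Annex 1.5 gives Q18 six points and Q18a six points. Q19, Q20, Q21 and Q22 each have one keyed answer. Total: 6 + 6 + 1 + 1 + 1 + 1 = 16. Annex 1.5 does not name the six Q18 points. I take them to be the six of the nine options that concern phototoxicity, skin or liver.

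**Step 2: match to the displayed page.**

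| Question | On the Q10 page | Directly cued items |
|---|---|---|
| Q18 | Sun avoidance, covering skin, sunscreen, dermatologic evaluation. Nothing on jaundice; detecting signs of phototoxicity is not given as advice to patients | 4 of 6 |
| Q18a | Sun-protection row only. Nothing on discussing the Patient Alert Card, monitoring advice, or the three rows on unrelated risks | 1 of 6 |
| Q19 | No liver-test content | 0 of 1 |
| Q20 | No liver-test content | 0 of 1 |
| Q21 | Same scenario and nearly the same wording as the keyed fourth option | 1 of 1 |
| Q22 | Stopping stated for SCC and premalignant lesions; for phototoxicity the page asks only that stopping be considered | Partial, direction unclear |

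Directly cued: 4 + 1 + 1 = 6 of 16 (37.5%). Q22 is not counted. Its key is the option combining all three conditions, and the page separates phototoxicity from the other two. A respondent following the page could be drawn towards or away from the keyed answer.

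**Step 3: what a cue could do to one item (assumed rates).** With n = 10, 80% means at least 8 HCPs. P(X ≥ 8) is the sum over k = 8, 9, 10 of C(10,k) p^k (1−p)^(10−k). For p = 0.6 this is 0.121 + 0.040 + 0.006 = 0.167. Annex 1.5 applies the 80% rule to the composite, so its use for a single item such as Q21 is only a yardstick.

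| Rate without cue → with cue | P(≥8 of 10) without → with |
|---|---|
| 0.60 → 0.90 | 0.167 → 0.930 |
| 0.70 → 0.95 | 0.383 → 0.988 |
| 0.80 → 1.00 | 0.678 → 1.000 |

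**Step 4: what it could do to the composite (assumed rates).** Let a be the probability that an HCP gets all six cued items right, and b the probability for the other ten, taken as independent. HCP success is a × b. The three entries in each cell use the three lifts in a from Step 3, in the same order.

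| b | P(≥8 of 10) without cue | with cue |
|---|---|---|
| 0.9 | 0.089 / 0.221 / 0.438 | 0.708 / 0.833 / 0.930 |
| 0.7 | 0.017 / 0.048 / 0.111 | 0.221 / 0.295 / 0.383 |
| 0.5 | 0.002 / 0.005 / 0.012 | 0.027 / 0.039 / 0.055 |

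The effect on the composite depends heavily on b. When the uncued items are answered poorly, the composite rarely reaches 80% with or without the cue.

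**The case against.** The other side has several fair points.

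- **A planned check exists.** Section 9.9.1 also promises to look for questions that suggest a particular answer. That is the right kind of control and might catch this. But the annex fixes the layout with the page in it, and the check as described concerns questions, not displayed images.
- **The image has a purpose.** It helps respondents recognise the tool, and Section 9.9.2 expects under-reporting of receipt. The Checklist's title is on the same page as Section A, so there may be no separate cover to show. This explains the choice, but a crop to the title keeps most of the benefit.
- **Non-recipients should be few.** Section 9.4.1 invites HCPs to whom the tools were handed. That reduces the contrast between recipients and non-recipients. It does not remove the cue for recipients who had forgotten the content.
- **Legibility is inferred.** The annex gives no display size. This stands, and the finding is conditional on it.
- **The study is descriptive.** There is no formal test, and the 80% threshold is described as subjective. This lowers the stakes, but the per-question proportions are themselves the reported result.

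A reader might go further and infer that the image gives away the whole block Q18 to Q22, that 7 of 16 items are answered by counting Q22, or that every respondent is biased upward. The documents do not support this. Q19, Q20, the jaundice option and five of the six Q18a rows are untouched; the direction for Q22 is unclear; and an HCP who would have answered desirably anyway cannot be moved up. Nor can it be said that the objective 4 verdict is inflated by a known amount, because one failed uncued item is enough to fail an HCP. Difficulty in attributing practice to the tools also comes from the single cross-sectional design without a comparator, not from the image alone.

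**Conclusion.** The point holds in limited form. The Q10 page shows Section A of the Checklist to all respondents before the practice questions, and directly cues about 6 of 16 scored items: four in Q18, one in Q18a, and Q21. Q22 is touched for two of its three conditions without a clear direction. The likely bias is upward for the cued skin items and will show mainly in the per-question results that Section 9.7 requires, with Q21 the most exposed. Its size cannot be derived from the documents; the probabilities above rest on assumed rates and, for the composite, on independence. The all-sub-questions rule limits the effect on the composite. The conclusion assumes that the image is legible on screen and that the six Q18 points are as read in Step 1.

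This should be corrected before programming. Section 9.6 allows no queries to respondents, so the cue cannot be removed once the surveys are in.

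**What to change.** Either of two changes is enough:

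1. At Q10, display only the Checklist title or header, in line with the images at Q9 and Q11.
2. Move Q18 to Q22 ahead of Q9. Keep the Patient Alert Card row of Q18a after Q11 and Q12, because it is routed on them.

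The first needs a cropped image. The second needs a reordered block and a split of Q18a. Neither adds a question. The cost of the crop is a slightly weaker visual recall aid for Q10; the reordering keeps the full image.

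If the layout stays as it is, Section 9.9.2 and the study report should name the cue as a limitation and identify the affected items, so that Q19 and Q20 can be read separately from the cued skin items. The wording of the displayed page on phototoxicity and the Q22 key should also be reconciled, since they treat that condition differently.
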